# 10.4.2 Primary Endpoint(s)

Table 10.4.2-1: Primary Endpoint

Primary Endpoint	Description	Timeframe
DLQI 0/1	Proportion of participants achieving DLQI score of 0 or 1	Week 16

DLQI, Dermatology Life Quality Index.

Table 10.4.2-2: Summary of Primary Endpoint

Endpoint	Statistical Analysis Methods
DLQI 0/1 response rate is defined as a proportion of participants with a DLQI score 0 or 1	The analysis model for the primary endpoint, DLQI $0/1$ (responder/non-responder) at Week 16, will use a stratified CMH test to compare the response rates of deucravacitinib 6 mg QD to placebo using the Week 16 data of the FAS population as well as the FAS subgroup where baseline s-PGA $\geq 3$ . If expected cell counts are not sufficient for each strata level, then strata levels will be combined for the analysis. The odds ratio (ratio of odds in deucravacitinib 6 mg QD to the odds in placebo group) and the corresponding 2-sided 95% CI will be provided. Estimates of proportions and their 2-sided 95% CIs will be provided.
	NRI will be used for the primary efficacy endpoint for participants who discontinue intervention or study prior to Week 16 or who have otherwise missing endpoint data at the specified timepoint. NRI will be the primary method of imputation for the primary efficacy endpoint.
	Sensitivity and supportive analyses to be performed for the primary endpoint will be described in the SAP.

CI, confidence interval; CMH, Cochran-Mantel-Haenszel; DLQI, Dermatology Life Quality Index; NRI, non-responder imputation; QD, once daily; SAP, statistical analysis plan; s-PGA, static Physician Global Assessment.

# 10.4.3 Secondary Endpoint(s)

**Table 10.4.3-1:** Summary of Key Secondary Endpoints

Endpoint	Statistical Analysis Methods	Time Frame
≥ 4-point reduction from baseline in DLQI is defined as a proportion of participants achieving at least a 4-point reduction from baseline in DLQI	The analysis model for $\geq$ 4-point reduction from baseline in DLQI (responder/non-responder) at Week 16, will use stratified CMH tests to compare the response rates of deucravacitinib 6 mg QD to placebo for the FAS population as well as the FAS sub-population where baseline s-PGA $\geq$ 3. If expected cell counts are not sufficient for each strata level, then strata levels will be combined for the analysis. The odds ratio (ratio of odds in deucravacitinib BMS-986165 6 mg QD to the odds in placebo group) and the corresponding 2-sided 95% CI will be provided. Estimates of proportions and their 2-sided 95% CIs will be provided. The NRI method will be applied to the analysis of the binary secondary efficacy endpoint for participants who discontinue early or who have otherwise missing endpoint data at the specified timepoint.	Week 16
Change from baseline in whole-body itch NRS score	The analysis model for the continuous secondary endpoint, change from baseline in whole-body itch NRS at Week 16, will use ANCOVA with intervention . The baseline value will be added into the model as a covariate. Intervention differences based on least-squares means and the corresponding 2-sided 95% CIs will be provided for the difference between deucravacitinib 6 mg QD and placebo for the FAS population as well as the FAS sub-population where baseline s-PGA $\geq 3$ . For the continuous secondary efficacy endpoint, multiple imputation will be used for missing data.	Week 16
Proportion of participants with a s-PGA score of 0	The analysis model for the secondary endpoint, s-PGA 0/1 (responder/non-responder) at Week 16, will use a stratified CMH) test to compare the response rates of deucravacitinib 6 mg QD to placebo using the	Week 16

Endpoint	Statistical Analysis Methods	Time Frame
(clear) or 1 (almost clear) with at least a 2-point reduction from baseline.	Week 16 data of the FAS sub-population where baseline $s-PGA \ge 3$ . If expected cell counts are not sufficient for each strata level, then strata level will be combined for the analysis. The odds ratio (ratio of odds in deucravacitinib 6 mg QD to the odds in placebo group) and the corresponding 2-sided 95% CI will be provided. Estimates of proportions and their 2-sided 95% CIs will be provided.	
	The NRI method will be applied to the analysis of the binary secondary efficacy endpoint for participants who discontinue early or who have otherwise missing endpoint data at the specified timepoint.	

ANCOVA, analysis of covariance; CI, confidence interval; CMH, Cochran-Mantel-Haenszel; DLQI, Dermatology Life Quality Index; FAS, Full Analysis Set; NRI, non-responder imputation; NRS, numerical rating scale; QD, once daily; s-PGA, static Physician Global Assessment.

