#### **Statistical Methods:**

There are 2 population groups of interest in this study. The Overall Population consists of all participants who were randomized to any treatment arm. The s-PGA  $\geq$  3 Sub-Population consists of all participants who were randomized to any treatment arm in the study with s-PGA  $\geq$  3 at baseline.

The 2 primary hypotheses will be tested simultaneously with a significance level (alpha) of 0.05 (2-sided). If either of the test results is not statistically significant (ie, at least one of null hypotheses is not rejected), then it is deemed that the study objective is not met. Key secondary endpoints will be tested in a hierarchical order only if the primary endpoint achieved statistical significance at the 2-sided 0.05 level on both the Overall Population and the s-PGA  $\geq$  3 Sub-Population. A hierarchical test may proceed to the next key secondary endpoint only if both null hypotheses within a key secondary endpoint are rejected.

The analysis model for the primary efficacy endpoint and secondary binary endpoint will use stratified Cochran-Mantel-Haenszel tests

to compare the response rates of deucravacitinib 6 mg QD to placebo. If expected cell counts are not sufficient for each strata level, then strata levels will be combined for the analysis. Non-responder imputation will be used for binary endpoints for participants who discontinue early or who have otherwise missing endpoint data at the specified timepoint. Sensitivity analyses to be performed for the primary endpoint will be described in the statistical analysis plan.

The analysis model for the continuous secondary endpoint will use analysis of covariance with study intervention

The baseline value will be added into the model as a covariate. Intervention differences based on least-squares means and the corresponding 2-sided 95% confidence intervals will be provided for the difference between deucravacitinib 6 mg QD and placebo.

For the continuous secondary efficacy endpoint, multiple imputation will be used for missing data.

The primary analysis at Week 16 will occur once all randomized participants completed their Week 16 visit or discontinued prior to Week 16. Analyses of the collected efficacy and safety data through Week 16 will be performed. A final analysis will be performed after all participants complete the final safety follow-up visit at Week 56 or post-discontinuation follow-up visit.

IM011237

Deucravacitinib

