# 3.1 Study Rationale

SOTYKTUTM (deucravacitinib), a first-in-class, oral, selective, allosteric tyrosine kinase 2 (TYK2) inhibitor is approved in multiple countries for the treatment of adults with moderate-to-severe plaque psoriasis who are candidates for systemic therapy or phototherapy. These approvals were based on the results of completed 52-week, randomized, Phase 3, placebo-controlled studies of deucravacitinib 6 mg daily (BMS-986165) versus placebo and apremilast 30 mg twice daily (BID) (POETYK PSO-1 and PSO-2).

In these 2 Phase 3 studies, in addition to achieving both co-primary clinical efficacy endpoints (PASI 75 and s-PGA 0/1), deucravacitinib also improved DLQI scores. Mean changes from baseline in DLQI were greater for deucravacitinib as early as Week 1 versus placebo in PSO-1 (-3.67 vs -2.18) and PSO-2 (-3.49 vs -2.82) and Week 4 versus apremilast in PSO-1 (-5.63 vs -4.83) and Week 8 in PSO-2 (-7.35 vs -6.31). More deucravacitinib-treated patients achieved  $\geq$  4-point improvement on DLQI meaningful change threshold (MCT  $\geq$  4) at Week 16 versus placebo-treated and apremilast-treated patients in PSO-1 (77.6% vs 43.4% and 68.8%, respectively) and PSO-2 (78.6% vs 44.9% and 69.3%). Similarly, higher responses versus apremilast were maintained through Week 24 in PSO-1 (79.5% vs 67.9%) and PSO-2 (79.2% vs 67.5%). In PSO-1, 81.6% achieved MCT  $\geq$  4 at Week 52 with continuous deucravacitinib treatment. Results were similar when applying an MCT  $\geq$  5. Higher DLQI 0/1 responses were seen with deucravacitinib vs apremilast and placebo arms at Week 16 in POETYK PSO-1 (40.7% vs 28.6% vs 10.6%) and POETYK PSO-2 (38.0% vs 23.1% vs 9.8%). Better DLQI 0/1 responses were also noted at Week 24 in deucravacitinib vs apremilast in POETYK PSO-1 (47.8% vs 24.2%)

and PSO-2 (38.0% vs 23.1%). At Week 52, 46.1% of patients in POETYK PSO-1 maintained their DLQI 0/1 score.

Additionally, this is a US-based study that aims to engage community-based dermatologists to facilitate a more diverse patient enrollment and to provide a more real-world patient population than was studied in Phase 3 studies.

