#### 5.2 Number of Participants

It is estimated that approximately 250 enrolled participants will be required to achieve 174 randomized. Approximately 174 participants will be randomized in a 2:1 fashion to deucravacitinib 6 mg QD or placebo matching deucravacitinib QD, respectively.

It is estimated that approximately 90% of randomized participants (ie, approximately 156 participants) would have baseline s-PGA scores  $\geq 3$ .

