#### 2) Type of Participant and Target Disease Characteristics

- a) Men and women diagnosed with stable plaque psoriasis for 6 months or more. Stable psoriasis is defined as no morphology changes or significant flares of disease activity in the opinion of the investigator.
- b) Deemed by the investigator to be a candidate for phototherapy or systemic therapy
- c)  $\geq 3\%$  of BSA involvement at the Screening Visit and Day 1
- d) DLQI score > 5 at the Screening Visit and Day 1
- e) Moderate-to-severe plaque psoriasis Day 1

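### The DLQI responder endpoints are tested by CMH, which cannot use continuous baseline DLQI; adjusting for it would bring a modest gain, mainly for the ≥ 4-point endpoint, unless the redacted strata already include a DLQI category

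*Combined protocol and SAP*

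**What the plan says.** For the primary endpoint, DLQI 0/1 at Week 16, Table 10.4.2-2 says that the analysis "will use a stratified CMH test to compare the response rates of deucravacitinib 6 mg QD to placebo using the Week 16 data". Table 10.4.3-1 gives the same method for the ≥ 4-point DLQI reduction: it "will use stratified CMH tests to compare the response rates of deucravacitinib 6 mg QD to placebo for the FAS population", and likewise for participants with baseline s-PGA ≥ 3. Both tables report an odds ratio with a 95% CI, use non-responder imputation, and allow strata to be combined when expected counts are too small. Table 10.4.1-1 names the odds ratio as the population-level summary for both endpoints.

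For the itch score, the same Table 10.4.3-1 specifies ANCOVA and states: "The baseline value will be added into the model as a covariate". The visible text has no corresponding sentence for the DLQI endpoints.

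Baseline DLQI is available for everyone, because entry requires "DLQI score > 5 at the Screening Visit and Day 1" (Section 6.1).

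Section 7.2 says that randomization is stratified, but the factors are not visible there, in the CMH descriptions or in the ANCOVA description. Section 10.4.2 leaves sensitivity and supportive analyses of the primary endpoint to the SAP.

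**The concern.** The ≥ 4-point response contains the baseline score in its definition. From 6, the lowest eligible score, a participant must reach 6 − 4 = 2 or less; from 20, 20 − 4 = 16 or less is enough. Unless the Week 16 score tracks baseline very closely, the chance of response varies with baseline for this reason alone. A CMH test can use baseline DLQI only if the score is cut into bands and the bands are made strata.

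At stake is some efficiency in the test and in the estimated difference in response rates. It would matter if the effect in this community population is smaller than in Phase 3, because each key secondary endpoint is reached only after both population tests at the step before it have succeeded. Validity is not at stake: the CMH test holds its level.

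**Working it through.** **Inputs from the documents.** Two-sided alpha 0.05. "Approximately 174 participants will be randomized in a 2:1 fashion to deucravacitinib 6 mg QD or placebo matching deucravacitinib QD, respectively", that is 116:58. The s-PGA ≥ 3 sub-population is about 0.90 × 174 = 156.6, stated as 156, that is 104:52. Section 3.1 gives Week 16 Phase 3 rates: DLQI 0/1 40.7% vs 10.6% (PSO-1) and 38.0% vs 9.8% (PSO-2); ≥ 4-point 77.6% vs 43.4% and 78.6% vs 44.9%. No target power or design rates are visible, so 174 itself cannot be reproduced.

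**Inputs assumed.** The documents do not say how strongly baseline DLQI predicts response. The simulations take baseline DLQI from 6 to 30, mean 12, SD about 4.5, and a within-arm correlation with Week 16 DLQI of 0.2 to 0.5. Because the strata are hidden, the comparator is an unstratified CMH.

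**Step 1. Power at the Phase 3 rates.** With p̄ = (2p₁ + p₀)/3:

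SE₀ = √[p̄(1 − p̄)(1/n₁ + 1/n₀)], SE₁ = √[p₁(1 − p₁)/n₁ + p₀(1 − p₀)/n₀], power = Φ[(p₁ − p₀ − 1.96·SE₀)/SE₁].

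For the ≥ 4-point endpoint, PSO-1, N = 174: p̄ = 0.662, SE₀ = 0.0761, SE₁ = 0.0757, and (0.342 − 0.149)/0.0757 = 2.55, so power is 99.5%.

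| Endpoint, source | N = 174 | N = 156 |
|---|---|---|
| ≥ 4-point, PSO-1 | 99.5% | 99.0% |
| ≥ 4-point, PSO-2 | 99.4% | 98.8% |
| DLQI 0/1, PSO-1 | 99.5% | 98.9% |
| DLQI 0/1, PSO-2 | 99.0% | 98.2% |

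There is little room for improvement here. In simulation, adjustment added less than 1 point.

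**Step 2. Variance of the response-rate difference.** The adjusted estimate is the standardised difference (1/N) Σ[p̂(1, xᵢ) − p̂(0, xᵢ)] from a logistic model with baseline DLQI x. Compared with the crude difference, at correlations of 0.2 to 0.5, its variance is about 5–16% lower for the ≥ 4-point endpoint and about 1–6% lower for DLQI 0/1. At N = 174, 5–16% is worth 174/0.95 − 174 = 9 to 174/0.84 − 174 = 33 participants. The result depends on the correlation: at 0.7 the gain for the ≥ 4-point endpoint shrinks to about 0–1%, while that for DLQI 0/1 rises to about 12%.

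**Step 3. Power if effects are smaller.** The rates in this table are assumptions, not figures from the documents.

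| Scenario | CMH | Logistic score test | CMH with three DLQI bands |
|---|---|---|---|
| ≥ 4-point, 66% vs 47%, N = 174 | 65–68% | 69–74% | 69–72% |
| Same, N = 156 | 62–63% | 65–70% | 64–68% |
| DLQI 0/1, 27% vs 12%, N = 174 | 64–65% | 66–69% | not used |

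The formula in Step 1 agrees. For 66% vs 47% at N = 174, SE₀ = SE₁ = 0.0789 and power is Φ(0.448) = 67.3%. Multiplying both variances by 0.95 gives 69.5%; multiplying by 0.84 gives 74.8%.

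**Step 4. Type I error.** The score test rejected in 4.3–5.5% of null trials and CMH in 4.3–5.4%. The choice of test matters. With a likelihood-ratio test and a baseline unrelated to outcome (DLQI 0/1, 30% vs 10.6%, N = 156), power still rose from 79.05% to 81.80%. Those 2.75 points come from the test and not from the covariate.

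**Step 5. The planned summary.** For the ≥ 4-point endpoint at PSO-1 rates and N = 174, the standard error of the log odds ratio rose with adjustment: from 0.347 to 0.375 when baseline had an odds ratio of 2.0 per SD, and from 0.348 to 0.392 at 2.5. The adjusted odds ratio is a different, conditional quantity, so power can rise although this standard error does not fall.

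**The case against.** The strongest objection is the redaction. The tests are stratified, and the factors cannot be seen. A reader might infer that the plan ignores baseline DLQI; the documents do not support that, because a DLQI category may be among the strata. If it is, most of the gain for the ≥ 4-point endpoint is already there, since bands kept most of it in Step 3. A baseline-adjusted supportive analysis of the primary endpoint may also be among those left to the SAP. Both points stand and make the recommendation conditional.

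A reader might also infer that CMH widens the interval for the planned odds ratio. Step 5 shows otherwise: the precision gain belongs to the rate difference, which is not the planned summary.

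Nor is adjustment free. CMH needs no assumption that the logit is linear in baseline DLQI. For DLQI 0/1 only about 58 × 0.106 = 6 or 52 × 0.098 = 5 placebo responders are expected, so extra strata thin cells that the plan already expects to combine.

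The need to succeed in both populations might suggest that the loss counts twice. The populations share about 156/174 = 90% of participants, so the two tests are strongly correlated.

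The argument might be extended to s-PGA 0/1. No calculation here supports that, and baseline s-PGA may itself be a stratum.

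Finally, ANCOVA for a continuous outcome and CMH for a binary one are both standard. The difference in method is not in itself an inconsistency.

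What survives is that CMH cannot use the continuous score, that the ≥ 4-point response depends on that score by definition, and that the score is already collected.

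**Conclusion.** The point holds in a limited, conditional form. In the visible text neither DLQI responder analysis uses continuous baseline DLQI. If no DLQI category is among the hidden strata, adjustment should lower the variance of the rate difference by about 5–16% for the ≥ 4-point endpoint and 1–6% for DLQI 0/1. That means roughly 2 to 6 points of power under the smaller effects examined, and less than 1 point at the Phase 3 rates.

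These figures rest on an assumed baseline–Week 16 correlation of 0.2 to 0.5, an assumed baseline distribution and an unstratified comparator. The benefit for the ≥ 4-point endpoint nearly vanishes if the correlation is about 0.7. The case for changing the ≥ 4-point analysis is reasonable; for the primary endpoint it is optional. Nothing here suggests that the planned CMH test is invalid or the trial underpowered at the cited rates.

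**What to change.** Before unblinding:

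1. Confirm whether a baseline DLQI category is among the randomization and CMH strata. If it is, little more is needed for the ≥ 4-point endpoint.
2. If it is not, pre-specify in Section 10.4.3 adjustment of the ≥ 4-point analysis for baseline DLQI in addition to the randomization strata. Use either a logistic model with continuous baseline DLQI and a score test for intervention, or preset DLQI bands as a further CMH stratum, stating the order in which strata are combined. The same may be done for DLQI 0/1 in Section 10.4.2.
3. Report the standardised response-rate difference with its 95% CI, and state that the adjusted odds ratio is conditional on baseline DLQI and the strata.
4. Say in Table 10.4.1-1 which odds ratio is meant.
5. Keep the current CMH as a sensitivity analysis.

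The cost is wording in Section 10 and the SAP; no new data are needed. The price is an odds ratio conditional on one more variable, plus either a linear-logit assumption or thinner cells.

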# 10.4.5 Safety Analysis

Safety data will be analyzed for AEs, SAEs, laboratory parameters, and vital signs. Safety will be summarized using the safety population. Categorical data will be summarized as frequency counts and percentages. Continuous data will be summarized using n, mean, standard deviation, median, minimum, and maximum unless otherwise specified. Safety will be analyzed through Week 16 and then up to end of study.

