## 5 STUDY DESIGN

## 5.1 Overall Design

This study (IM011237) is a Phase 4, multicenter, randomized, double-blind, placebo-controlled study to evaluate the effect of deucravacitinib on QoL in patients with plaque psoriasis and impaired HRQoL. A total of approximately 174 qualified participants with moderate-to-severe

plaque psoriasis will be randomized. It is estimated that approximately 90% of randomized participants (ie, approximately 156 participants) would have baseline s-PGA scores  $\geq 3$ .

The duration of study participation is approximately 60 weeks and will be divided into the following periods: screening (up to 4 weeks), intervention (52 weeks), and safety follow-up (4 weeks).

Physical examination (PE), clinical laboratory evaluations, and other assessments will be done at select visits during the study. Participants in this study will be monitored for AEs.

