## 7.2 Method of Study Intervention Assignment

Before the study is initiated, each user (at investigative sites) will receive log-in information and directions on how to access the IRT system. At the time of the Screening Visit, immediately after informed consent is obtained and before any study-related procedures are performed, the investigative site will access the enrollment option of the IRT system for assignment of a participant number for all participants, including participants not subsequently randomized or treated. The participant number is assigned sequentially by the system and will be unique across all sites. All enrolled participants will be assigned sequential participant numbers. The participant number will not be used for any other participant. If a participant is rescreened, they will be given a new identification number.

At Day 1, participants who meet all criteria for enrollment at Screening and Day 1 will be centrally randomized in a 2:1 ratio to deucravacitinib 6 mg QD or placebo as determined by a computer-generated randomization schedule using IRT. The randomization lists will be generated by the IRT vendor using a permuted block design within each stratum level.

After all inclusion/exclusion criteria have been met for a participant, the investigative site will access the IRT on Day 1 for the purpose of randomizing a participant. An intervention group will be assigned by IRT based on the above-described randomization schedule. In addition, a unique kit number will be assigned to the participant corresponding to the intervention assignment.

Study intervention will be dispensed at study visits as shown in the Schedule of Activities (Section 2). When new intervention kits need to be provided, the investigative site will access the IRT to obtain the kit number to assign to the participant.

At Week 16, all participants, regardless of their blinded intervention, will be switched to open-label deucravacitinib 6 mg QD bottles through Week 52.

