Analysis set for secondary estimand of whole-body itch NRS	All randomized participants; all available data up to Week 16 database lock. Participants who discontinue prior to Week 16 will be imputed using multiple imputation in the analysis dataset. Following the intent-to-treat principle, participants will be analyzed according to the intervention group assigned at randomization.
	All randomized participants with baseline s-PGA $\geq$ 3; all available data up to Week 16 database lock. Participants who discontinue prior to Week 16 will be imputed using multiple imputation in the analysis dataset. Following the intent-to-treat principle, participants will be analyzed according to the intervention group assigned at randomization.
Analysis set for secondary estimand of s-PGA 0/1	All randomized participants with baseline s-PGA $\geq$ 3; all available data up to Week 16 database lock. Participants who discontinued prior to Week 16 will be imputed as non-responders in the analysis dataset. Following the intent-to-treat principle, participants will be analyzed according to the intervention group assigned at randomization.
Analysis set for safety	All safety events reported for all randomized participants who are exposed to study intervention. For participants who discontinue study intervention all post-discontinuation up to day 28 post last dose of study intervention will be included in the safety summaries.  Participants will be analyzed according to intervention received.

DLQI, Dermatology Life Quality Index; FAS, Full Analysis Set; NRS, Numerical Rating Scale; s-PGA, static Physician Global Assessment.

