#### 10.4.1 General Considerations

Categorical data will be summarized as frequency counts and percentages. Continuous data will be summarized using n, mean, standard deviation, median, minimum, and maximum unless otherwise specified. Efficacy values will be summarized for all visits in which the variable is assessed. Baseline values are defined as the last non-missing value prior to the first dose of study drug unless otherwise indicated.

During the first 16 weeks of treatment, data will be presented for the following interventions:

- Deucravacitinib 6 mg QD
- Placebo

After Week 16, data will be presented for the following interventions:

- Deucravacitinib 6 mg QD
- Placebo- deucravacitinib 6 mg QD (starting at Week 16 through Week 52)

The primary endpoint, DLQI 0/1 response, is defined as a proportion of participants achieving DLQI score of 0 or 1 at Week 16. The key secondary endpoints assessed at Week 16 are  $\geq$  4-point reduction from baseline in DLQI, change from baseline in whole-body itch NRS score and s-PGA 0/1 response. s-PGA 0/1 is defined as a proportion of participants with a s-PGA score of 0 (clear) or 1 (almost clear) with at least a 2-point reduction from baseline at Week 16.

Table 10.4.1-1: Definition of Estimands for Primary and Key Secondary Endpoints

Primary Endpoint			
Estimand Attribute	Definition		
Treatment	Deucravacitinib 6 mg QD v	ersus placebo	
Population	FAS population and FAS su	b-population	
Variable	DLQI 0/1		
ICEs	Event	Strategy	Description
	Discontinuation of intervention or study early prior to Week 16 assessment	Composite variable	Participant will be counted as a non-responder
	Lost to follow-up prior to Week 16 or otherwise missing endpoint data at Week 16 assessment	Composite variable	Participant will be counted as a non-responder
	Start a protocol prohibited medication/therapy	Treatment policy	Participants will be included in the primary analysis regardless of the occurrence of the ICE according to the respective endpoint definition.
	Missing assessment at Week 16 due to SARS-CoV-2	While on treatment	Participants will be excluded from the primary analysis if the Week 16 assessment was not completed due to SARS-CoV-2
Population-level Summary	Odds ratio of achieving DLQI 0/1		

Table 10.4.1-1: Definition of Estimands for Primary and Key Secondary Endpoints

Key Secondary Endpoi	nts			
Estimand Attribute	Definition			
Treatment	Deucravacitinib 6 mg QD versus placebo			

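### End-of-study safety is summarised only as counts and percentages over an undefined window, although planned time on deucravacitinib is 52 weeks in one arm and 36 in the other

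*Combined protocol and SAP*

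**What the plan says.** Section 10.4.5 (Safety Analysis) gives the measure: "Categorical data will be summarized as frequency counts and percentages". It gives the windows in one sentence: "Safety will be analyzed through Week 16 and then up to end of study". Section 10.4.5.1 tabulates adverse events by MedDRA system organ class and preferred term, and mentions no person-time denominator. Section 10.4.6 (Other Analyses) is marked not applicable.

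Section 7.2 describes the switch: "At Week 16, all participants, regardless of their blinded intervention, will be switched to open-label deucravacitinib 6 mg QD bottles through Week 52". Section 5.1 gives the periods as "screening (up to 4 weeks), intervention (52 weeks), and safety follow-up (4 weeks" weeks).

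Section 10.4.1 divides presentation at Week 16. Up to then the columns are deucravacitinib and placebo. For the later period it says "After Week 16, data will be presented for the following interventions", and lists deucravacitinib 6 mg QD and a switch column, "Placebo- deucravacitinib 6 mg QD (starting at Week 16 through Week 52").

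Table 10.3-1 in Section 10.3 groups the safety population by treatment taken: "Participants will be analyzed according to intervention received". For those who stop treatment, it counts events up to day 28 after the last dose.

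**The concern.** A crude percentage is the share of participants with at least one event in whatever time each was observed. It compares columns fairly only when time at risk is similar. Here the arms have different planned time on active drug, and the 28-day limit after the last dose makes time at risk vary within each arm as well. For example, a participant who stops at Week 8 contributes about 12 weeks (8 + 4), while one who completes contributes 56 (52 + 4). Both count as one in the denominator.

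At stake is how the 52-week safety results can be read. Depending on how the table is built, a difference between columns could reflect exposure rather than risk, or a real difference between placebo and active drug could be diluted. In addition, no summary described in the protocol puts all deucravacitinib exposure on one time scale.

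**Working it through.** **Inputs from the protocol**
- Periods: 4 + 52 + 4 weeks (Section 5.1).
- Visit days: Day 1, D113 (Week 16), D365 (Week 52) (Tables 2-2 and 2-3).
- Size: about 174 randomised 2:1 (Section 5.2), so 116 and 58.
- Event window after stopping: 28 days (Table 10.3-1).

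**Assumed, because the protocol gives no adverse event rate:** a constant rate of first events, equal on active drug in both arms, and no dropout. Rates from 0.02 to 3 per person-year are shown.

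**Reproducing the plan's durations.** 4 + 52 + 4 = 60 weeks and 60 × 7 = 420 days, as in Section 5.3. D365 − D1 = 364 days = 52 weeks. D113 − D1 = 112 days = 16 weeks. D365 − D113 = 252 days = 36 weeks. Planned active exposure is therefore 52 vs 36 weeks.

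**Formula.** Percentage with an event = 1 − exp(−rate × weeks / 52).

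**Reading 1: cumulative from first active dose (52 vs 36 weeks)**

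| Rate per person-year | 52 weeks | 36 weeks | Ratio |
|---|---|---|---|
| 0.02 | 2.0% | 1.4% | 1.44 |
| 0.1 | 9.5% | 6.7% | 1.42 |
| 0.2 | 18.1% | 12.9% | 1.40 |
| 0.5 | 39.3% | 29.3% | 1.34 |
| 1 | 63.2% | 50.0% | 1.27 |
| 3 | 95.0% | 87.5% | 1.09 |

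The ratio cannot exceed 52/36 = 1.44. It is largest for rare events and shrinks for common ones. With 28 days of follow-up added, the windows are 56 vs 40 weeks and the limit is 56/40 = 1.40.

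**Reading 2: Day 1 to end of study by randomised arm (52 vs 52 weeks).** If the rate is the same on placebo and active drug, the percentages are equal. If the active rate is 0.4 and the placebo rate 0.2:
- deucravacitinib arm: 1 − exp(−0.4) = 33.0%
- switch arm: 1 − exp(−(0.2 × 16 + 0.4 × 36)/52) = 28.7%

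The ratio is 33.0/28.7 = 1.15 although the rates differ twofold, because 36 of the switch arm's 52 weeks are on active drug.

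**Reading 3: Weeks 16 to 52 only (36 vs 36 weeks).** Equal rates give equal percentages, for example 6.7% vs 6.7% at 0.1. The table then omits the first 16 active weeks of the deucravacitinib arm: 116 × 16/52 = 35.7 person-years. Total planned active exposure is 116 × 52/52 + 58 × 36/52 = 116 + 40.2 = 156.2 person-years, so 35.7/156.2 = 23% is left out.

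**With exposure-adjusted incidence.** Divide first events by person-years up to first event or censoring. At 0.2 per person-year, with cumulative active windows:
- 52 weeks: 0.181 events over 0.181/0.2 = 0.906 person-years per participant
- 36 weeks: 0.129 events over 0.129/0.2 = 0.647 person-years per participant

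Both give 20.0 per 100 person-years, where the crude percentages were 18.1% and 12.9%.

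**The case against.** A reader might infer that the end-of-study tables will make equal event rates look different. The documents do not support that as a statement of fact. Section 10.4.1 lists both later columns under the period after Week 16, which is 36 vs 36 planned weeks. A Day 1 table by randomised arm is 52 vs 52. The 52 vs 36 comparison arises only if the deucravacitinib column starts at Day 1 and the switch column at Week 16. Grouping by intervention received makes such a table plausible, but it is not stated.

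Other parts of the opposing case also stand. Reporting the placebo arm as placebo before Week 16 and as a switch group afterwards is already largely planned. The stated secondary safety objective covers Week 0 to Week 16, where planned exposure is equal. No between-column test of end-of-study safety is described. The sizes above rest on assumed rates. Section 10.4 also says that a SAP will be written, and its text is not available here, so it may supply person-time rates.

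This does not remove the point. Section 10.4.5 does not choose among the three readings, and crude percentages fall short under each. It also contains no deferral to the SAP, whereas Section 10.4.2 defers its sensitivity analyses explicitly and the deferral in Section 10.6 follows the description of the Week 16 analysis.

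**Conclusion.** The point holds as a low-severity improvement. The protocol names counts and percentages as the only measure for categorical end-of-study safety data and leaves the start of the window open. If the table is cumulative on active drug, exposure alone could produce a ratio of up to about 1.44. The absolute gap depends on the assumed rate: 2.8 points at 10 per 100 person-years and about 10 points at 50. If the table covers Weeks 16 to 52 only, the gap from planned exposure is zero, but 23% of planned active person-time is missing and early discontinuation is still ignored.

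These figures assume constant, equal rates and full follow-up. A rate that changes with time on drug would alter them. The randomised Week 0 to 16 safety comparison and all efficacy results are unaffected.

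**What to change.** In Section 10.4.5 (or the SAP):
- Keep percentages for the randomised Week 0 to 16 comparison.
- State the start, end and denominator of the end-of-study window.
- Assign the placebo arm's events and person-time to placebo before the first open-label dose and to deucravacitinib after it.
- Add exposure-adjusted incidence per 100 person-years, with time counted to first event or censoring.
- Add one pooled any-deucravacitinib column, covering about 156 person-years if everyone completes.

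Section 7.6 already has intervention start and stop dates recorded in the CRF, so no new data or participants are needed. The cost is a few extra descriptive table columns.
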